2.2. Endpoints

2.2.1. Primary Endpoints

The primary endpoints are:

- The number and percentage of study participants who experience solicited local and systemic reactions during the 7 days after administration of investigational M2SR vaccine or placebo, as recorded through subject electronic diary (eDiary).
- The number and percentage of study participants who experience unsolicited AEs during the 28 days after administration of investigational M2SR vaccine or placebo and prior to administration of licensed QIV.
- The number and percentage of study participants who experience SAEs from the time of informed consent through 28 days after receipt of QIV.

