2.2.2. Secondary Endpoints

The secondary endpoints are:

- The number and percentage of study participants who experience unsolicited AEs during the 28 days after administration of licensed QIV.
- The number and percentage of study participants who after administration of Sing2016 M2SR or placebo and before administration of QIV demonstrate:
 - Influenza-specific serum antibody responses measured in MN and hemagglutination inhibition (HAI) assays at specified time points.
 - Influenza-specific mucosal immunoglobulin A (IgA) antibody responses measured in enzyme-linked immunosorbent assay (ELISA) assays at specified time points.

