8.2. Secondary

Immunogenicity will be assessed by measuring serum antibody responses by MN and/or HAI assay and mucosal antibody titers by ELISA. Additional immune parameters may be assessed including T cell responses. Samples are collected pre dose, at Day 29, and Days 1 and 29 QIV. Sample collection dates/times will be recorded in the clinical database.

Immunogenicity analyses will be analyzed as randomized. Additional details for specific immunogenicity assays may be added to this SAP as immunogenicity analyses are finalized.

Serum antibody response (influenza-specific HAI, MN, NAI, and ELISA results) will be summarized by treatment comparisons of GMT, GMFR, seroconversion, and seroprotection.

GMTs and GMFRs are displayed below by visit. Note that for approximately 40% of subjects, beginning at the end of September 2021, IP Day 29 and QIV Day 1 sample collection was on the same day.

Geometric Mean Titers and Mean Folds by Visit

Sample Collection	GMT	GMFR – reference
IP Day 1	X	
IP Day 29	X	IP Day 1
QIV Day 1	X	IP Day 1
QIV Day 29	X	QIV Day 1 & IP Day 1

Ln-transformed GMT and the ln-transformed GMFR ratios will be analyzed using t-tests. In case of baseline imbalance between treatments, analyses may be repeated using a general linear model adjusting for baseline titers.

Conversion rates categorized as >=2-fold and >= 4-fold will be reported for IP Day 29 and QIV Day 29. Treatment comparisons of conversion counts (%) will be done using Fishers Exact Tests. In case of baseline imbalance between treatments, analyses may be repeated using a logistic regression adjusting for baseline titers.

Seroprotection defined as HAI titer >=40 will be reported for IP Day 29 and QIV Day 29. Treatment comparisons of seroprotection counts (%) will be done using Fishers Exact Tests. In case of baseline imbalance between treatments, analyses may be repeated using a logistic regression adjusting for baseline titers.

Summary statistics for IgA response to influenza HA antigens are presented uncorrected and corrected for total IgA.

For the uncorrected analysis all samples are included regardless of total IgA(ug/mL).

For IgA corrected analysis

- \circ If Total IgA >= 1 then corrected value = Uncorrected/Total IgA.
- o If Total IgA < 1 then set the corrected value to missing.

For example: SingC = Sing / Total IgA >= 1; Else SingC = missing.

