9.2. Adverse Events (AEs)

Adverse events were to be recorded from the day of informed consent through QIV Day 29. For subjects without QIV administration, follow-up for both AEs and SAEs was 28 days after IP. During the study treatment period subjectswere asked non-leading questions to determine the occurrence of spontaneously reported (unsolicited) AEs.

Symptoms were collected for the 7 days following IP administration using eDiaries, with clinical interpretation of data entries by the site investigator. At the discretion of the investigator, a symptom recorded by the subject on the eDiary may have been reported as an AE. The investigator was responsible for determining the severity and the relationship to IP for any eDiary-based AEs. There was no reconciliation of the database between the eDiary symptoms and other AE reports.

PE findings recorded as clinically significant, severe, or life threatening were to be recorded as AEs. Investigators usedtheir judgement regarding reporting of additional PE findings as AEs.

All AEs will be included in the listings. Only treatment emergent AEs will be summarized.

Separate listings of subjects who died, discontinued the study due to an AE, or experienced an SAE will be provided.

Treatment-emergent AEs (TEAE) are AEs with start dates between administration of the IP and IP Day29. If there is no administration of QIV then AE/SAE follow-up will be 28 days post IP administration. However, AEs with start dates past Day 29, if judged by the investigator to be IP-related, will be included in the treatment emergent set.

All AEs will be coded based on MedDRA (V24.0).

Where provided in Protocol Appendix 1, AEs will be graded according to the Vital Sign and Systemic Toxicity Assessments.

N (%) of subjects with at least one TEAE and N (%) of subjects with at least one treatment-related treatment-emergent AE (TRAE) will be summarized. TEAE and TRAE by worst severity will be summarized.

N (%) of subjects with TEAE will be reported by System Organ Class and Preferred Term (SOC/PT) and maximum severity. N (%) of subjects with TRAE will be reported by SOC/PT and maximum severity.

N (%) of subjects with TEAE by SOC/PT by overall frequency (decreasing) will be reported.N (%) of subjects with TRAE will be reported by SOC/PT by overall frequency (decreasing).

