AEs will be reported by start date as: a) following IP administration, b) after IP administration and before QIV administration, c) within 7 days of IP administration, and d) after QIV administration.

No statistical test comparing adverse event rates will be done.

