9.4. Vital Signs

Blood pressures, heart rate, respiratory rate and temperature will be summarized at each time point by descriptive statistics for the result and for the change from baseline (IP and then QIV baseline).CS values or CS change from Baseline were recorded as AEs at the discretion of the clinical investigator.

Vital signs were graded according to the FDA Guidance for Industry: Toxicity Grading Scale for Healthy Adult and Adolescent Volunteers Enrolled in Preventive Vaccine Clinical Trials, September 2008, and noted as clinically significant. Vital signs to be assessed include: fever, tachycardia, bradycardia, systolic and diastolic hypertension, diastolic hypotension, and respiratory rate. These VS will be reported by shift tables of worst grade recorded post IP administration through QIV Day 29.

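### SAP 9.2 ends the treatment-emergent window at IP Day 29 without a pre-QIV cut-off, conflicts with its own post-QIV reporting line, and gives the primary SAE endpoint only a listing

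*SAP*

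**What the plan says.** **Endpoints.** Protocol 2.2.1 has two primary endpoints that matter here. One counts subjects with unsolicited AEs in the 28 days after IP, and only up to the point at which QIV is given. The other is "The number and percentage of study participants who experience SAEs from the time of informed consent through 28 days after receipt of QIV". Protocol 2.2.2 adds a secondary endpoint: "The number and percentage of study participants who experience unsolicited AEs during the 28 days after administration of licensed QIV". It serves the first secondary objective, the safety of QIV after M2SR.

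**AE analysis.** SAP 9.2 states: "Treatment-emergent AEs (TEAE) are AEs with start dates between administration of the IP and IP Day29". The one extension is that "AEs with start dates past Day 29, if judged by the investigator to be IP-related, will be included in the treatment emergent set". It also states: "Only treatment emergent AEs will be summarized". The TEAE and related-TEAE tables (any event, worst severity, SOC/PT, frequency) all rest on that definition. SAEs, deaths and AE discontinuations get listings.

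**Reporting periods.** The end of SAP 9.2 says AEs will be reported by start date in four periods, among them "b) after IP administration and before QIV administration, c) within 7 days of IP administration, and d) after QIV administration".

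**Populations.** SAP 2.1.1.3 defines a QIV safety set (QIVSS). It appears again as a disposition count in SAP 3. SAP 9 is headed with the IP safety set (IPSS), and no safety table is assigned to QIVSS.

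**Timing.** SAP 8.2 notes that for roughly 40% of subjects "IP Day 29 and QIV Day 1 sample collection was on the same day". Footnote 1 to Protocol Table 3 permits V03 and V04 to be combined once 28 days have passed since V01.

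**The concern.** SAP 1 makes the SAP prevail where it disagrees with the protocol, so the SAP's definitions decide which events enter which table. Three things follow from the text.

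1. Two statements in SAP 9.2 point in different directions on AEs after QIV. A programmer cannot build the secondary endpoint without choosing between them and supplying details that the SAP does not state.
2. The IP-period definition differs from the primary endpoint it is meant to serve, because it does not stop at QIV administration. On a shared visit day, a reaction to the QIV injection can be counted as emergent after IP, in either arm.
3. A primary endpoint defined as a number and percentage has no summary output.

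Safety is the primary objective of this trial, so these are the tables on which its main conclusion rests.

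**Working it through.** The plan states no figure on this point, so there is none to reproduce. The check sets endpoints against outputs, followed by simple arithmetic.

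**Step 1. Endpoint against planned output**

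| Endpoint (Protocol 2.2) | Output in SAP 9.2 | Gap |
|---|---|---|
| Unsolicited AEs, 28 days after IP and before QIV (primary) | TEAE tables, onset from IP to IP Day 29 plus later IP-related AEs | No pre-QIV cut-off; period b) has one, but the main tables do not use it |
| SAEs, consent to 28 days after QIV (primary) | Listing | No N (%) for any window |
| Unsolicited AEs, 28 days after QIV (secondary) | Period d) | No stated N (%), 28-day limit or population; conflicts with the TEAE-only rule |

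**Step 2. The two readings of period d)**

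- If the TEAE-only rule governs, period d) can hold only AEs judged IP-related, plus onsets on a shared Day 29 after the injection. That is not the secondary endpoint.
- If the period list governs, period d) covers all AEs after QIV, but the endpoint's 28-day limit is not applied. Protocol Table 3 places V05 at QIV Day 29 ±7, and AEs are monitored until V05 (Protocol 6.2.3). The latest in-window visit is Day 29 + 7 = Day 36, which is 35 days after QIV. AEs with onset beyond 28 days can therefore enter.

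**Step 3. Same-day overlap**

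Inputs: planned N = 120, with 80 active and 40 placebo (SAP 1.1.1); same-day share about 40% (SAP 8.2).

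- Subjects with a shared day: 0.40 × 120 = 48. If the share is equal by arm (an assumption), 0.40 × 80 = 32 active and 0.40 × 40 = 16 placebo.
- Study Day 1 is the IP day, so 28 days after V01 is Day 29. V03 is Day 29 ±3 (Protocol Table 2), so a combined visit within the V03 window falls on Days 29 to 32.
- If IP Day 29 means the visit, all 48 shared days lie in the TEAE window. If it means the calendar day, only those falling exactly on Day 29 do. The SAP does not say which, so 48 is an upper bound on subjects exposed to the overlap.
- Only AEs starting on that day after the injection are affected. The documents give no rate. For illustration, assume that 1% to 20% of these subjects have such an AE:
  - 48 × 0.01 = 0.48 subjects, and 0.48 / 120 = 0.4%
  - 48 × 0.20 = 9.6 subjects, and 9.6 / 120 = 8%
- The rise in the any-TEAE percentage would be smaller still, because a subject who already had a TEAE in the preceding 28 days is not counted again.

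**Step 4. SAEs**

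An SAE between consent and IP, or after Day 29 and not judged IP-related, is not a TEAE and so falls outside every TEAE summary. The period list does not mention SAEs. The listing is the only SAE output named.

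**The case against.** The strongest counter-argument is that post-QIV safety reporting was plainly intended. Period d) refers to AEs, not TEAEs. QIVSS exists for safety results. Protocol 8.3 expects separate post-IP and post-QIV summaries, and the synopsis names the safety of the licensed QIV alone. The IPSS heading of SAP 9 is not exclusive either, since SAP 9.2.1 uses the IP evaluable set. This stands. A reader might infer from the TEAE-only rule that post-QIV AEs are not reported at all. The documents do not support that: the defect is a conflict and an under-specified output.

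A reader might also infer that QIV reactions in 40% of subjects flow into the IP tables. That is too strong. QIV reactions starting on later days are outside the window unless judged IP-related, or unless a calendar Day 29 window is read in place of the visit. No diary is used after QIV, so same-day onsets depend on unsolicited reporting. Period b) already has the correct cut-off. The main TEAE, SOC/PT and severity tables nevertheless use the definition without it.

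On SAEs, the listing supplies a numerator and SAP 3 supplies set sizes, so a count could be assembled by hand. Protocol 8.3.2 also plans listings. Even so, a primary endpoint expressed as a number and percentage should have its own stated output and denominator.

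Finally, the study is descriptive, with no test of AE rates. That lowers the consequences but does not remove the mismatch between definitions and endpoints.

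**Conclusion.** The point holds as an inconsistency and an under-specification, in three parts.

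- **Post-QIV AEs:** the TEAE-only rule and the period list in SAP 9.2 conflict, and the secondary endpoint lacks a stated N (%), 28-day limit and population.
- **IP-period AEs:** the definition departs from the primary endpoint by omitting the pre-QIV limit. At most about 48 of 120 subjects are exposed, and only for onsets on the shared day after injection. The number of events is not given and is probably small; the 0.4% to 8% range rests wholly on an assumed 1% to 20% rate.
- **SAEs:** no N (%) is specified for a primary endpoint. This part depends on no assumption and is not repaired elsewhere in the SAP.

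The first and third parts hold whatever the same-day event rate is.

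**What to change.** Amend SAP 9.2 as follows.

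1. **IP period (IPSS):** onset from IP administration to the earlier of 28 days after IP or QIV administration. On a shared day, split by onset time, or by a pre/post-QIV flag where the time is missing. State that Day 29 is a calendar day. If later IP-related AEs are kept, show them separately.
2. **QIV period (QIVSS):** onset from QIV administration to 28 days after it, as N (%) by randomized-period IP arm received, with the same SOC/PT, severity and relatedness tables.
3. **SAEs:** one N (%) table from consent through 28 days after QIV, with the denominator stated, including how subjects who never receive QIV are counted.
4. **Reconciliation:** reword the TEAE-only rule so that it agrees with the four-period list.

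The cost is SAP wording, a few extra tables and a same-day onset flag. The AE and SAE data are already collected through QIV Day 29, and trial conduct does not change.

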The purpose of this proposed, additional Phase 1b clinical study is to assess for the first time the safety, tolerability/reactogenicity, and immunogenicity of H3N2 monovalent M2SR vaccines in an older adult population. A group of 15 adults age 50-64 will be enrolled first to assess safety. The probability that an AE with prevalence of 20% or more would be detected in the 15 subjects is >95%. After a safety review, the study will enroll 105 adults ages 65 to 85 years of age. One dose of investigational vaccine will be given intranasally followed at least 28 days later by delivery of an age-appropriate licensed QIV that is a quadrivalent influenza vaccine (QIV) recommended for the 2021/2022 season. Licensed vaccines will be selected and supplied by the Sponsor so that all subjects, within an age cohort, receive the same vaccine product. The same Sing2016 M2SR vaccine that will be used in this study has previously been investigated in adults 18-49 years of age, as described above. Demonstration of broadly reactive responses in the older adult population, similar to those found to be protective against challenge in adults, would support further clinical development of the M2SR vaccine platform in this age group.

Consistent with CDC recommendations, all subjects participating in the study will receive the licensed influenza vaccine at least 28 days after administration of study investigational product

(IP). The timing of the administration of licensed vaccine also will depend upon the availability of licensed vaccine, which usually occurs by early September each season. It is anticipated that the window between IP and QIV administrations for subjects in Cohorts 1 and 2 will be more variable, but no less than 28 days. The first cohort is anticipated to receive the first dose of IP in June 2021, but QIV may not be available until September. The window for administration of licensed QIV to study participants in Cohort 3 will be 28 to 42 days after intranasal administration of M2SR. Subjects will be followed for AEs occurring within 28 days after intramuscular inoculation with the licensed product. Subject diaries will not be employed after licensed vaccine administration.

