6.2.3. Adverse Events

Adverse events will be monitored regularly from informed consent until Visit 05 (28 days after QIV administration). At regular intervals during the study, subjects will be asked non-leading questions to determine the occurrence of any AEs. All AEs reported spontaneously during the study will be recorded as well. Solicited and unsolicited signs and symptoms will be reported as AEs after review by the Investigator or designee, either separately using the corresponding Medical Dictionary for Regulatory Activities (MedDRA) terminology of the sign or symptom or combined using the appropriate term. For example, a subject who reported concurrent cough, runny nose, and sneezing assessed by the Investigator as unrelated to vaccine should have those symptoms grouped as a syndromic diagnosis (URI), with the severity based on the most severe AE/symptom. Therefore, as a secondary presentation, subjects with 3 or more concurrent unrelated AEs of cough, runny nose/rhinorrhea, sneezing, sore throat, itchy throat, itchy eyes, congestion, nasal irritation, hoarseness, headache, body aches/myalgia, tiredness/fatigue, malaise, and fever will have those AEs grouped as URI.

For detailed definitions and reporting procedures of AEs, see Section 9.

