9. ADVERSE EVENT REPORTING

9.1. **Definitions**

Adverse Event

An AE is any untoward medical occurrence in a clinical study subject administered a medicinal (investigational or non-investigational) product. An AE does not necessarily have a causal relationship with the treatment. An AE can therefore be any unfavorable and unintended sign (including an abnormal finding), symptom, or disease temporally associated with the use of a medicinal (investigational or non-investigational) product, and whether related to that medicinal (investigational or non-investigational) product.

This includes any occurrence that is new in onset or aggravated in severity or frequency from the baseline condition, or abnormal result of diagnostic procedures, including clinical laboratory test abnormalities.

AEs will be monitored from the time of consent until Visit 03 (Day 28 after the IP dose administration) and from Visit 04 until Visit 05 (Day 28 after the QIV dose administration). SAEs or medically attended events will be documented from the time of consent until Visit 05.

Serious Adverse Event

An SAE is any untoward medical occurrence that meets any of the following conditions:

- results in death;
- is life-threatening, i.e., the subject was at risk of death at the time of the event (e.g., ventricular fibrillation and anaphylaxis). The term does not refer to an event which hypothetically might have caused death if it were more severe.
- requires inpatient hospitalization or prolongation of existing inpatient hospitalization:
 - Hospitalization refers to an overnight admission into hospital for the purpose of investigating and/or treating the AE. Hospitalization for an elective procedure, or routinely scheduled treatment for a pre-existing condition that has not worsened, is not an SAE.
- results in persistent or significant disability/incapacity, i.e., causing substantial disruption of the subject's ability to conduct normal life;
- is a congenital anomaly/birth defect;
- is medically significant, i.e., may not be immediately life-threatening or result in death or hospitalization but may jeopardize the subject's health or may require intervention to prevent one of the above outcomes. Examples of such events are intensive treatment in an emergency room or at home for allergic bronchospasm, blood dyscrasias, or convulsions that do not result in hospitalization or development of drug dependency or drug abuse.

Unlisted (Unexpected) Adverse Event

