1.1. Statistical and Analytical Plans

1.1.1. Definitions and General Considerations for Data Analysis

- 1. This Statistical Analysis Plan (SAP) is based on Clinical Trial Protocol FluGen-H3N2-V002-V005 dated 10-May-2021 (v2.0).
- 2. All programming and calculations will be performed using SAS statistical software, version 9.4 or later.
- 3. Study Day 1 is the day of randomization and 1st IP administration; QIV administration is planned 28 Days after IP administration
- 4. Baseline (IP Baseline) is the last observation prior to IP administration, at the datapoint, not the record level. For example, for laboratory values, individual repeat tests values will be used for baseline when the entire panel may not have been repeated.
- 5. Summaries will be presented by treatment and age group and for all ages combined. Cohorts 2 and 3 will not be presented separately.
- 6. This study is not powered to detect differences in safety or immunogenicity between active and placebo groups. The sample size of 120 (80 active subjects and 40 placebo subjects) was chosen empirically based on studies of other vaccines in early-stage development.
- 7. There is no plan for test of hypotheses; p-values generated for immunogenicity are descriptive only and not adjusted for multiplicity.
- 8. For transparency and traceability, raw data, not results from calculations or corrections are to be transferred from external vendors. Differences between data transferred versus data as analyzed, will be documented in the CSR.
- 9. The clinical database will be locked prior to final analyses of immunogenicity assays. Details regarding these analyses may be included as amendments to this SAP.

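### SAP 9.2 counts AEs between IP and QIV over an interval of no fixed length and does not say whether its start-date categories are limited to treatment-emergent AEs; the protocol also contradicts itself on AE collection in that interval

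*SAP*

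**What the plan says.** SAP 9.2 lists four reporting categories by AE start date: "AEs will be reported by start date as: a) following IP administration, b) after IP administration and before QIV administration", then (c) the first 7 days after IP and (d) the time after QIV. No length is given for (b), and no statistic or denominator is stated for any of the four.

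Protocol 1.4 sets the length of (b) indirectly. For the expansion cohort: "The window for administration of licensed QIV to study participants in Cohort 3 will be 28 to 42 days after intranasal administration of M2SR". For the others, "the window between IP and QIV administrations for subjects in Cohorts 1 and 2 will be more variable, but no less than 28 days". The same section expects Cohort 1 to receive IP in June 2021, with QIV possibly unavailable until September. Protocol 3.1 allows QIV until early November 2021.

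Cohort 1 is the only cohort aged 50-64 (protocol Table 1). SAP 1.1.1 says "Summaries will be presented by treatment and age group and for all ages combined", with Cohorts 2 and 3 merged.

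Earlier in SAP 9.2, summaries are restricted to TEAEs. These are AEs starting between IP and IP Day 29, plus later AEs judged IP-related.

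The documents differ on whether routine AEs were collected between V03 and V04:
- Protocol 9.1: "AEs will be monitored from the time of consent until Visit 03 (Day 28 after the IP dose administration) and from Visit 04" to Visit 05, with only SAEs and medically attended events documented throughout.
- Protocol 6.2.3: "Adverse events will be monitored regularly from informed consent until Visit 05 (28 days after QIV administration"). SAP 9.2 likewise describes recording from consent through QIV Day 29.

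**The concern.** Safety is the primary objective, no AE test is planned, and this is the platform's first use in older adults, so readers will rely on the displayed counts. If (b) covers all AEs, its length follows the QIV supply calendar. Because the longest waits are expected in the cohort that makes up the whole 50-64 column, a difference between age columns could come from observation time alone. The pooled level of (b) would also move with supply dates.

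The other reading has a different cost. Protocol 2.2.2 makes unsolicited AEs in the 28 days after QIV a secondary endpoint. A TEAE restriction would leave category (d) almost nothing to count.

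The conflict over collection between V03 and V04 affects what (b) can contain at all.

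**Working it through.** **The plan's own AE figure.** Protocol 1.4 gives more than 95% probability of seeing an AE of 20% prevalence among 15 subjects: 1 − 0.8^15 = 0.965. It reproduces and is not in dispute. It is the only AE design figure in the documents; no expected AE rate is given.

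**Length of category (b).**
- Cohort 3: 28 to 42 days (protocol 1.4).
- Cohort 1, June IP and September QIV: 30 June to 1 September is 63 days; 1 June to 1 September is 92; 1 June to 30 September is 121.
- Outer planned limit, taking early November as 7 November (assumption): 1 June to 7 November is 159 days.

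These come from planned dates, not actual ones.

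**How common a gap is.** SAP 8.2 says about 40% of subjects had IP Day 29 and QIV Day 1 samples on the same day, so about 60% did not. The gap after Day 29 is at most 42 − 28 = 14 days in Cohort 3, and 63 − 28 = 35 to 121 − 28 = 93 days in Cohort 1 on the June and September dates.

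**Reading 1: categories limited to TEAEs.** Category (b) is capped at Day 29 apart from late IP-related events, so unequal waits matter little. But QIV is given at least 28 days after IP. Category (d) could then hold only late IP-related AEs and any AE starting on Day 29 after a same-day QIV.

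**Reading 2: all AEs, collected continuously.** For illustration, let p be an assumed 28-day risk and the hazard constant. Risk over t days = 1 − (1 − p)^(t/28):

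| p | 28 d | 42 d | 63 d | 92 d | 121 d |
|---|---|---|---|---|---|
| 0.10 | 0.100 | 0.146 | 0.211 | 0.293 | 0.366 |
| 0.20 | 0.200 | 0.284 | 0.395 | 0.520 | 0.619 |
| 0.40 | 0.400 | 0.535 | 0.683 | 0.813 | 0.890 |

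For the age columns take p = 0.20 and Cohort 1 waits of 60 to 92 days:
- 50-64: 1 − 0.8^(60/28) = 0.38; 1 − 0.8^(92/28) = 0.52.
- 65-85, assuming 15 Cohort 2 subjects wait 14 days less than Cohort 1 (46 or 78 days), all 48 same-day subjects (40% of 120) are in Cohort 3 at 28 days, and the other 42 are at 35 days. Mean wait = (15×46 + 42×35 + 48×28)/105 = 33.4 days, or with 78 in place of 46, 37.9 days. Risk at those means: 0.23 and 0.26.
- Ratio: 0.38/0.23 = 1.6 to 0.52/0.26 = 2.0, with identical underlying risk.

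As a cross-check, put all 15 Cohort 2 subjects at 92 days. The 65-85 column is then 0.25 with all of Cohort 3 at 28 days and 0.32 with all at 42 days, against 0.52 for 50-64.

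**Reading 3: all AEs, collected as protocol 9.1 describes.** Routine AEs end at V03 for everyone, so the numerator covers about 28 days plus SAEs and medically attended events. The unequal wait adds little, but the label on (b) overstates what was observed: at a 92-day wait, 92 − 28 = 64 days have no routine collection.

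Readings 2 and 3 exclude each other for any one subject, so their effects do not add.

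**The case against.** The strongest reply is that the fixed window already exists. The TEAE definition runs from IP to Day 29, and the N (%) tables itemised in SAP 9.2 are TEAE or treatment-related TEAE tables. They, not category (b), are closest to the primary unsolicited-AE endpoint in protocol 2.2.1. This stands, so a reader who infers that the primary safety tables rest on an elastic window would be wrong. It does not settle (a) to (d): the presence of (d) suggests they reach beyond TEAEs, and the SAP does not say.

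A reader might also infer that age-group percentages for (b) are planned and non-comparable. The SAP states no percentages for (a) to (d), and SAP 8.7 plans no subgroup analysis. Presentation by age group is planned; an age contrast is not. Cohort 1 has only 10 active subjects, so 2 of 10 would carry an exact 95% interval of about 3% to 56%.

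A third tempting reading is that AE collection definitely stopped at V03. Protocol 9.1 says so, but protocol 6.2.3 and SAP 9.2 say otherwise, and SAP section 1 gives the SAP precedence. Precedence governs the analysis; it cannot supply events that a site following 9.1 did not record. Nothing shows that sites differed in practice.

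Finally, constant hazard is doubtful. Diary symptoms from the first 7 days may be reported as AEs, which would front-load events and shrink the ratio. That is fair.

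**Conclusion.** The point holds as a defect in one display and an inconsistency between sections. Category (b) has no fixed length, its length is tied to the age-group columns by design, and its population is unstated. Each reading has a cost: TEAEs only removes the substance of (d) and leaves the post-QIV secondary endpoint without a real summary; all AEs with continuous collection makes (b) depend on QIV supply dates.

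The 1.6- to 2-fold apparent age difference is an illustration. It needs continuous collection, a constant hazard, the assumed 20% risk and the assumed waits, and it should not be quoted as an expected bias.

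Vaccine versus placebo is protected by randomisation within cohort. The TEAE tables are affected only through late IP-related AEs. The conflict over collection between V03 and V04 is a separate matter: it replaces the unequal-time problem rather than adding to it.

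**What to change.** In SAP 9.2:
1. State that (a) to (d) cover all AEs, and make this an explicit exception to the rule that only TEAEs are summarised.
2. Replace (b) with IP administration to the earlier of Day 29 and QIV, and (d) with QIV administration to QIV Day 29.
3. Report events between Day 29 and QIV in a separate table, with the number of subjects and person-days in the gap.

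Reconcile protocol 9.1 with protocol 6.2.3 and SAP 9.2. The SAP is dated June 2022 and describes AE recording in the past tense, so new wording cannot change what was collected. The practical step is to document in the SAP or CSR what sites recorded between V03 and V04. If 9.1 was followed, limit the gap table to SAEs and medically attended events.

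The AE start dates that SAP 9.2 already uses are enough, with dosing dates, so no new data are needed. The downside is one small extra table.
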